### Indications and Usage:

Revlimid® (lenalidomide) is indicated for the treatment of patients with transfusion-dependent anemia due to Low- or Intermediate-1-risk myelodysplastic syndromes associated with a deletion 5q cytogenetic abnormality with or without additional cytogenetic abnormalities. Revlimid® is also approved in combination with dexamethasone for the treatment of patients with multiple myeloma that have received at least one prior therapy. Revlimid is also for the treatment of patients with mantle cell lymphoma (MCL) whose disease has relapsed or progressed after two prior therapies, one of which included bortezomib.

### Adverse Events

Most frequently reported adverse events reported during clinical studies with lenalidomide in oncologic and non-oncologic indications, regardless of presumed relationship to study

[figure not shown]
medication include: anemia, neutropenia, thrombocytopenia and pancytopenia, abdominal pain, nausea, vomiting and diarrhea, dehydration, rash, itching, infections, sepsis, pneumonia, UTI, Upper respiratory infection, atrial fibrillation, congestive heart failure, myocardial infarction, chest pain, weakness, hypotension, hypercalcemia, hyperglycemia, back pain, bone pain, generalized pain, dizziness, mental status changes, syncope, renal failure, dyspnea, pleural effusion, pulmonary embolism, deep vein thrombosis, CVA, convulsions, dizziness, spinal cord compression, syncope, disease progression, death not specified and fractures.

Complete and updated adverse events are available in the Investigational Drug Brochure and the IND Safety Letters.

### **Lenalidomide Description**

REVLIMID® (lenalidomide), a thalidomide analogue, is an immunomodulatory agent with anti-angiogenic properties. The chemical name is 3-(4-amino-1-oxo 1,3-dihydro -2H-isoindol-2-yl) piperidine-2,6-dione and it has the following chemical structure:

Chemical Structure of Lenalidomide

3-(4-amino-1-oxo 1,3-dihydro-2H-isoindol-2-yl) piperidine-2,6-dione

The empirical formula for lenalidomide is C13H13N3O3, and the gram molecular weight is 259.3.

Lenalidomide is an off-white to pale-yellow solid powder. It is soluble in organic solvent/water mixtures, and buffered aqueous solvents. Lenalidomide is more soluble in organic solvents and low pH solutions. Solubility was significantly lower in less acidic buffers, ranging from about 0.4 to 0.5 mg/ml. Lenalidomide has an asymmetric carbon atom and can exist as the optically active forms S(-) and R(+), and is produced as a racemic mixture with a net optical rotation of zero.

### **Clinical Pharmacology**

#### **Mechanism of Action:**

The mechanism of action of lenalidomide remains to be fully characterized. Lenalidomide possesses immunomodulatory and antiangiogenic properties. Lenalidomide inhibited the secretion of pro-inflammatory cytokines and increased the secretion of anti-inflammatory cytokines from peripheral blood mononuclear cells. Lenalidomide inhibited cell proliferation with varying effectiveness (IC50s) in some but not all cell lines. Of cell lines tested, lenalidomide was effective in inhibiting growth of Namalwa cells (a human B cell lymphoma

cell line with a deletion of one chromosome 5) but was much less effective in inhibiting growth of KG-1 cells (human myeloblastic cell line, also with a deletion of one chromosome 5) and other cell lines without chromosome 5 deletions. Lenalidomide inhibited the expression of cyclooxygenase-2 (COX-2) but not COX-1 in vitro.

## **Pharmacokinetics and Drug Metabolism**

### **Absorption:**

Lenalidomide, in healthy volunteers, is rapidly absorbed following oral administration with maximum plasma concentrations occurring between 0.625 and 1.5 hours post-dose. Co-administration with food does not alter the extent of absorption (AUC) but does reduce the maximal plasma concentration (Cmax) by 36%. The pharmacokinetic disposition of lenalidomide is linear. Cmax and AUC increase proportionately with increases in dose. Multiple dosing at the recommended dose-regimen does not result in drug accumulation.

Pharmacokinetic analyses were performed on 15 multiple myeloma patients treated in the phase I studies. Absorption was found to be rapid on both Day 1 and Day 28 with time to maximum blood levels ranging from 0.7 to 2.0 hours at all dose levels (5mg, 10mg, 25mg, and 50mg). No plasma accumulation was observed with multiple daily dosing. Plasma lenalidomide declined in a monophasic manner with elimination half-life ranging from 2.8 to 6.1 hours on both Day 1 and 28 at all 4 doses. Peak and overall plasma concentrations were dose proportional over the dosing range of 5mg to 50mg **Error! Reference source not found.** Exposure (AUC) in multiple myeloma patients is 57% higher than in healthy male volunteers.

## **Pharmacokinetic Parameters**

### **Distribution**

In vitro (C)-lenalidomide binding to plasma proteins is approximately 30%.

## **Metabolism and Excretion**

The metabolic profile of lenalidomide in humans has not been studied. In healthy volunteers, approximately two-thirds of lenalidomide is eliminated unchanged through urinary excretion. The process exceeds the glomerular filtration rate and therefore is partially or entirely active. Half-life of elimination is approximately 3 hours.

### **Supplier(s)**

Celgene Corporation will supply Revlimid® (lenalidomide) to study participants at no charge through Celgene's Revlimid Risk Evaluation and Mitigation Strategy™ (REMS) (formerly known as RevAssist® Program).

### **Dosage form**

Lenalidomide will be supplied as capsules for oral administration.

## **Packaging**

Lenalidomide will be shipped directly to patients or to the clinic site. Bottles will contain a sufficient number of capsules for one cycle of dosing.

## **Labeling**

Lenalidomide supplies are dispensed in individual bottles of capsules. Each bottle will identify the contents as study medication. In addition, the label will bear Celgene's name, quantity contained and the standard caution statement as follows: "Caution: New drug - Limited by Federal law to investigational use." Lenalidomide should not be handled by FCBP unless wearing gloves.

The study drug label must be clearly visible. Additional labels must not cover the Celgene label.

## **Receipt of study drug**

The Investigator or designee is responsible for taking an inventory of each shipment of study drug received, and comparing it with the accompanying study drug accountability form. The Investigator will verify the accuracy of the information on the form, sign and date it, retain a copy in the study file, and return a copy to Celgene or its representative.

## **Storage**

Lenalidomide should be stored at room temperature away from direct sunlight and protected from excessive heat and cold.

## **Unused study drug supplies**

Celgene will instruct the Investigator on the return or destruction of unused study drug. If any study drug is lost or damaged, its disposition should be documented in the source documents. Study drug supplies will be retained at the clinical site pending instructions for disposition by Celgene. Patients will be instructed to return empty bottles or unused capsules to the clinic site.

## **Special Handling Instructions**

Females of childbearing potential should not handle or administer lenalidomide unless they are wearing gloves.

## Prescribing Information

Lenalidomide (Revlimid®) will be provided to research subjects for the duration of their participation in this trial at no charge to them or their insurance providers. Lenalidomide will be provided in accordance with the Celgene Corporation's Revlimid REMS® program. Per standard Revlimid REMS® program requirements, all physicians who prescribe lenalidomide for research subjects enrolled into this trial, and all research subjects enrolled into this trial, must be registered in, and must comply with, all requirements of the Revlimid REMS® program.

**Only enough lenalidomide for one cycle of therapy will be supplied to the patient each cycle.**

## Pregnancy Testing

Must follow pregnancy testing requirements as outlined in the Revlimid REMS® program material.

## 3.0 PATIENT SELECTION

### 3.1 Inclusion Criteria:

1. Patients aged 18 to 55 years with high risk (as defined in #2) AML who have achieved their **FIRST** CR or CRi within 12 months of enrollment and are not immediately candidates for allogeneic stem cell transplant. Patients above age 55 who are not eligible for other protocols may be considered for enrollment on a case by case basis after discussion with the PI.
2. Patients in their **FIRST** CR or CRi may be eligible for enrollment only if they have a high risk feature, including, but not limited to: adverse karyotype, FLT3 mutation, history of antecedent hematologic disorder (AHD), presence of dysplasia in the bone marrow, therapy-related AML, history of requiring more than 1 cycle of intensive induction chemotherapy to achieve first remission, or presence of persistent minimal residual disease (detected by cytogenetics, molecular markers, or flow cytometry) at any point after initial induction cycle. Patients aged > or = 18 years with AML who have achieved a **SECOND** CR or CRi within 12 months of enrollment and are not immediately candidates for allogeneic stem cell transplant are also eligible.
3. Patients should have received induction chemotherapy for AML and at least 1 consolidation.
4. Patients with history of extramedullary AML, except for CNS involvement that is currently controlled, will not be eligible for enrollment.
5. ECOG performance status of < or = 3
6. Adequate organ function as follows:
  - a. Serum total bilirubin < or = to 1.5 X the Upper Limit of Normal (ULN)
  - b. Serum creatinine < or = to 2.5 x ULN
7. Adequate BM reserve:
  - a. Absolute neutrophil count (ANC) > 0.5 x 10^9/L
  - b. Platelet count > or = 30 x 10^9/L

## Prescribing Information

Lenalidomide (Revlimid®) will be provided to research subjects for the duration of their participation in this trial at no charge to them or their insurance providers. Lenalidomide will be provided in accordance with the Celgene Corporation's Revlimid REMS® program. Per standard Revlimid REMS® program requirements, all physicians who prescribe lenalidomide for research subjects enrolled into this trial, and all research subjects enrolled into this trial, must be registered in, and must comply with, all requirements of the Revlimid REMS® program.

**Only enough lenalidomide for one cycle of therapy will be supplied to the patient each cycle.**

## Pregnancy Testing

Must follow pregnancy testing requirements as outlined in the Revlimid REMS® program material.

## 3.0 PATIENT SELECTION

### 3.1 Inclusion Criteria:

1. Patients aged 18 to 55 years with high risk (as defined in #2) AML who have achieved their **FIRST** CR or CRi within 12 months of enrollment and are not immediately candidates for allogeneic stem cell transplant. Patients above age 55 who are not eligible for other protocols may be considered for enrollment on a case by case basis after discussion with the PI.
2. Patients in their **FIRST** CR or CRi may be eligible for enrollment only if they have a high risk feature, including, but not limited to: adverse karyotype, FLT3 mutation, history of antecedent hematologic disorder (AHD), presence of dysplasia in the bone marrow, therapy-related AML, history of requiring more than 1 cycle of intensive induction chemotherapy to achieve first remission, or presence of persistent minimal residual disease (detected by cytogenetics, molecular markers, or flow cytometry) at any point after initial induction cycle. Patients aged > or = 18 years with AML who have achieved a **SECOND** CR or CRi within 12 months of enrollment and are not immediately candidates for allogeneic stem cell transplant are also eligible.
3. Patients should have received induction chemotherapy for AML and at least 1 consolidation.
4. Patients with history of extramedullary AML, except for CNS involvement that is currently controlled, will not be eligible for enrollment.
5. ECOG performance status of < or = 3
6. Adequate organ function as follows:
  - a. Serum total bilirubin < or = to 1.5 X the Upper Limit of Normal (ULN)
  - b. Serum creatinine < or = to 2.5 x ULN
7. Adequate BM reserve:
  - a. Absolute neutrophil count (ANC) > 0.5 x 10^9/L
  - b. Platelet count > or = 30 x 10^9/L

8. For females of childbearing age, they may participate if they:
  - a. Have a negative serum or urine pregnancy test within 10 to 14 days of enrolling  
(A second pregnancy test will be performed within 24hrs of starting therapy and both negative pregnancy tests will be required for starting therapy.)
  - b. Agree to either abstinence or 2 effective contraceptive methods throughout the treatment period and up to 28 days after discontinuing treatment.
9. For male patients with a female partner of childbearing age, they may participate if they agree to either abstinence or 2 effective contraceptive methods throughout the treatment period and up to 28 days after discontinuing treatment.
10. All study participants must be willing and able to comply with the requirements of the REMS® program.
11. Females of reproductive potential must be willing to adhere to the scheduled pregnancy testing as required in the Revlimid REMS® program.
12. Ability to understand and sign informed consent.

### 3.2 Exclusion Criteria

1. Diagnosis of acute promyelocytic leukemia (APL), AML - M3 by FAB classification based on morphology, immunophenotype, molecular, or cytogenetic studies.
2. Diagnosis of AML associated with the following karyotypes: inv(16), t(16;16), t(8;21), or t(15;17). Patients with t(9;22) are also ineligible unless they are unable or unwilling to receive therapy with a tyrosine kinase inhibitor.
3. Uncontrolled intercurrent illness including, but not limited to ongoing or active uncontrolled infection, symptomatic congestive heart failure, unstable angina pectoris, cardiac arrhythmia, or psychiatric illness/social situations that would limit compliance with study requirements.
4. Patients with active CNS disease.
5. Previous treatment with lenalidomide for AML.
6. Patients with documented hypersensitivity to any components of the study program.
7. Females who are pregnant.

## 4.0 TREATMENT PLAN

This is a single arm, open label phase II clinical trial evaluating low intensity, continuous dosing of lenalidomide in patients with *high risk* AML who have responded to induction/consolidation therapy and are NOT immediately candidates for stem cell transplant.

Treatment will be continued during the duration of the study, up to 24 months unless patient exhibits evidence of clinically significant treatment failure, clinically significant disease progression, unacceptable toxicity, treatment with stem cell transplantation, or if the investigator determines that discontinuation is in the best interest of the patient. Relapsing patients (that is not clinically significant) may remain on the study if participation in the study is still providing clinical benefit and is considered in the best interest of the patient after discussion with the principal investigator.

Patients will be treated with the study drug per protocol, based on fixed dosing as outlined below.

The objective is to determine the effect of lenalidomide maintenance on relapse free survival (RFS), overall survival (OS), and CR duration in patients with high risk AML in remission. We will also determine toxicity and tolerability of this regimen, as well as the effect of lenalidomide maintenance on NK cell biology and the dynamics of minimal residual disease.

All patients will be registered for the protocol via the Clinical Oncology Research (CORe) system at MDACC (single institution study).

#### 4.1 Treatment Schema

##### 4.1.1 Maintenance Lenalidomide Dosing:

Lenalidomide continuous dosing on days 1- 28 of a 28 day cycle.

Dose of lenalidomide is as follows:

- Starting dose (DOSE LEVEL 0): 10mg orally daily during cycle 1
- If after one cycle, the patient has persistent evidence of (1) minimal residual disease or (2) morphologically active disease AND is tolerating their starting dose of lenalidomide, their dose may be increased to the next higher dose level for the remainder of the study. A maximum of 2 dose escalations per patient are allowed if well tolerated.

Table 1. Dose escalation and de-escalation table.

Dose Level	Lenalidomide Dosing
-2	5 mg PO Every other Day
-1	5 mg PO Daily
0 (Starting dose level)	10 mg PO Daily
1	15 mg PO Daily
2	20 mg PO Daily

One cycle of therapy is considered 28 days. Therapy will be continuous; interruptions and dose-adjustments for toxicity will be implemented as needed.

#### 4.2 Supportive Care Measures during treatment

Necessary supportive measures for optimal medical care can be given throughout the study as indicated by the treating physician's assessment of the patient's medical need and by the institutional guidelines. Administration of antiemetics during drug administration and throughout treatment course is permitted as clinically indicated and according to departmental guidelines. Blood products should be transfused as indicated and in accordance with institutional guidelines. The use of other anti-leukemia therapy is not allowed during the course of therapy. Concomitant

intrathecal chemotherapy and/or radiation therapy is permitted where indicated in patients with extramedullary disease.

#### 4.2.1 Hematopoietic growth factors

Hematopoietic growth factors such as filgrastim (GCSF) or pegfilgrastim is permitted as clinically indicated at the discretion of the treating physician.

#### 4.2.2 Infection prophylaxis

Antibacterial, antifungal, and antiviral agents may be used in patients being treated on this study in accordance with the standard of care.

### 4.3 Duration of Therapy

In the absence of treatment delays due to adverse events, the treatment will be administered continuously for a total of 24 months. The patient will continue on the study unless one of the following criteria applies:

- Clinically significant progressive disease as defined by Modified International Working Group Criteria (**see section 9**).
- Undergoing allogeneic bone marrow transplant.
- Intercurrent illness that prevents further administration of treatment.
- Patient request.
- Unacceptable toxicity.
- Need for alternative treatment.
- General or specific changes in the patient's condition that render the patient unacceptable for further treatment in the judgment of the investigator or treating physician.

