## 5.2 During treatment Evaluation.

- a. Physical examination (including vital signs, weight, performance status) every 28 days ( $\pm 7$  days) for the first 3 months, then every 3 months until 12 months from the start of therapy; then every 6 months ( $\pm 2$  months).
- b. CBC with differential (differential not required if  $WBC \leq 0.5 \times 10^9/L$ ), at least once weekly for the 1st cycle, then every 2 to 4 weeks during cycles 2-6, and then every 4 weeks ( $\pm 14$  days) thereafter as long as they are on study.
- c. Serum chemistry profile at least once weekly for the 1st cycle, then every 2 to 4 weeks during cycles 2-6, and then at least every 4 weeks ( $\pm 14$  days) during active treatment.
- d. Bone marrow aspiration and/or biopsy after cycle 1, after 3 months of therapy ( $\pm 2$  weeks), then every 3 months ( $\pm 1$  month) until month 12, then every 6 months ( $\pm 2$  months). No repeat bone marrow is necessary if non-response or progressive disease can be unequivocally diagnosed from peripheral blood tests or, in patients with a  $WBC < 0.4 \times 10^9/L$ , if the bone marrow is considered non-contributory by the investigator at any point.
- e. Flow cytometry for MRD after cycle 1, after 3 months of therapy ( $\pm 2$  weeks), then every 3 months ( $\pm 1$  month) until month 12, then every 6 months ( $\pm 2$  months).
- f. Peripheral blood for correlative immune studies once weekly for the 1st cycle, and once at the end of cycle 3, 6, and 12. (if patient agrees to correlatives)
- g. Patients will be followed for survival every 6 to 12 months after completion of active treatment and while still on study or be enrolled on the leukemia department long-term follow-up umbrella protocol.
- h. Women of child bearing potential must have a negative pregnancy test prior to each cycle of therapy.

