### **9.1.6 Confirmed Relapse**

Recurrence of disease as noted by: > 30% peripheral blasts, or > 20% bone marrow blasts. If the bone marrow blasts are between 6% and 20%, 2 serial bone marrow examinations at least 2 weeks apart demonstrating successive increase in blasts by at least 2% will also be a confirmed relapse.

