### **9.1.7 Relapse-free survival (RFS)**

Time from CR or CRi until confirmed relapse or death.

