### **9.1.8 Event-free survival (EFS)**

Time from treatment start until date of first documented event. Event will be defined as: confirmed relapse, withdrawal from study due to adverse event, or death due to any cause.

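### Section 8 and Section 9 define the primary RFS event differently, and a patient stopped after one unconfirmed 6-20% blast marrow has no RFS, EFS or CRd event at that time under Section 9

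*Combined protocol and SAP*

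**What the plan says.** **Stopping.** Section 4.3 ends treatment for "Clinically significant progressive disease as defined by Modified International Working Group Criteria", with a pointer to Section 9, and separately for "Need for alternative treatment". Section 9 defines CR, CRi, PR and confirmed relapse. It does not define progressive disease.

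**Relapse.** Section 9.1.6 counts more than 30% peripheral blasts or more than 20% marrow blasts at once. Between 6% and 20% it asks for "2 serial bone marrow examinations at least 2 weeks apart demonstrating successive increase in blasts by at least 2" per cent.

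**Endpoints in Section 9.** RFS is "Time from CR or CRi until confirmed relapse or death". EFS runs from treatment start to "confirmed relapse, withdrawal from study due to adverse event, or death due to any cause". CRd (9.1.9) ends only at confirmed relapse.

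**Primary endpoint in Section 8.** RFS runs from treatment start to death or relapse, without the word confirmed. Patients alive and relapse-free are censored at last follow-up, and transplanted patients at transplant. No rule covers other new anti-leukemia therapy.

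**Follow-up.** On treatment, Section 5.2(d) schedules marrows after cycle 1, at month 3, then 3-monthly to month 12, then 6-monthly. Off treatment, Section 5.2(g) says "Patients will be followed for survival every 6 to 12 months after completion of active treatment" and, as the continuation, "while still on study or be enrolled on the leukemia department long-term follow-up umbrella protocol".

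**The concern.** Take a patient whose scheduled marrow shows 15% blasts, who is judged to need other therapy and stops. Section 4.3 permits this after one marrow. Section 9.1.6 does not yet call it a relapse, and no further marrow is scheduled. Read with Section 8, this could be a primary event on the date of that marrow. Read with 9.1.7, it is not an event at that time. EFS and CRd are defined only in Section 9, so no reading of Section 8 repairs them. EFS counts withdrawal for an adverse event but not withdrawal for progression.

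A delayed or missing event lengthens apparent RFS. The trial is single-arm and open-label, and its primary analysis is Pr(λE > λH + 2.5 | data) against a historical prior with mean 8 months. The same event count drives the futility rule.

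**Working it through.** **Model (Section 8).** RFS is exponential. With d events and S total follow-up months, the posterior is λE ~ IG(2.128 + d, 9.024 + S·ln 2), and λH ~ IG(3.6, 20.8). The prior moments check:
- λH: mean 20.8/2.6 = 8; variance 8²/1.6 = 40.
- λE: mean 9.024/1.128 = 8; variance 8²/0.128 = 500.

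**The plan's own figures.** Simulated early-stopping probabilities (2 patients per month, 5000 trials, first look with 11 patients already enrolled) against the Section 8 table:

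| True median (months) | 4 | 6 | 8 | 10.5 | 12 |
|---|---|---|---|---|---|
| Plan | 0.968 | 0.410 | 0.102 | 0.030 | 0.017 |
| Reproduced | 0.969 | 0.408 | 0.104 | 0.032 | 0.016 |

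**Assumption.** Let f be the share of RFS events that are stops after an unconfirmed marrow. The documents do not give f.

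**Direction.** The estimated median is ln 2 · S/d. Censoring at the stop leaves S as it was and reduces d to (1 − f)d, so a true median of 8 becomes 8/(1 − f): 8/0.9 = 8.9, 8/0.8 = 10.0 and 8/0.7 = 11.4 months.

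**Final analysis.** True median 8, 50 patients at 1 per month plus 12 months. With f = 0 the mean posterior is about 0.38 and the apparent median about 8.0. Each cell gives the mean posterior, then the apparent median in months where available. The delays are assumed medians after the stop.

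| What happens after the stop | f = 10% | f = 20% | f = 30% |
|---|---|---|---|
| Relapse confirmed, 1 month | 0.39; 8.1 | 0.40; 8.3 | 0.41; 8.4 |
| Relapse confirmed, 2 months | 0.40 | 0.43 | 0.45 |
| Carried to death, 3 months | 0.41; 8.4 | 0.45; 8.7 | 0.48; 9.0 |
| Carried to death, 6 months | 0.45; 8.7 | 0.51; 9.3 | 0.57; 9.9 |
| Carried to death, 12 months | 0.50; 9.2 | 0.60; 10.4 | 0.68; 11.6 |
| Censored at the stop | 0.47; 8.9 | 0.57; 10.0 | 0.66-0.67; 11.4 |

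With f = 3-5%, carried to death at 6 months, the posterior is 0.40-0.41. Adding 25% transplant censoring changes the posterior by 0.01 or less.

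**Futility, censored at the stop (f = 0, then 10/20/30%).**
- True median 4: 0.97, then 0.89/0.73/0.50.
- True median 6: 0.42, then 0.29/0.17/0.10.
- True median 8: 0.13, then 0.08/0.05/0.03.

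These runs took the first look at the arrival of patient 10, so the 8-month baseline of 0.13 sits above the plan's 0.102. Read the shifts, not the levels. They also assume that no relapse is confirmed later.

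**The case against.** The strongest reply is that Section 4.3 refers to Section 9, whose only recurrence category is confirmed relapse, so both Section 4.3 and the word relapse in Section 8 should be read as confirmed relapse. That reading is natural, and it would settle the primary definition. It does not close the gap: the alternative-treatment stop still needs no confirmation, and the two RFS definitions also differ on time origin, so Section 8 does not simply import 9.1.7.

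Second, patients with low blast counts may well stay on drug. Section 4.0 lets a relapse that is not clinically significant continue, and 4.1.1 allows a higher dose for morphologically active disease. Many would then be confirmed at a later marrow. This stands, and f could be small.

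Third, a reader might infer that these patients can only wait for death or be censored. The documents do not support that: 9.1.6 does not limit confirmation to the treatment period, so a later documented relapse counts. At a median of 1-2 months to confirmation, the posterior shift is only about 0.02 to 0.07 for f = 10-30%.

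Fourth, a reader might see another leak in Section 5.2(d): "No repeat bone marrow is necessary if non-response or progressive disease can be unequivocally diagnosed from peripheral blood tests". That route is weak. The diagnosis must be unequivocal, and the only blood criterion given is above 30% blasts, which is itself a confirmed relapse.

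Finally, confirmation at 6-20% is a deliberate rule. Counting a single marrow plus an investigator's decision to stop brings judgment into an open-label endpoint and, if the history used confirmed relapse, would bias against the drug. This is a fair cost and is why a confirmed-only analysis is needed alongside.

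**Conclusion.** The point holds as a conflict of definitions together with a follow-up gap, and should be fixed. For a patient stopped after one 6-20% marrow, Section 9 gives no event at that time, Section 8 could give one, and the plan does not choose. CRd has no end date for such a patient unless a later relapse is recorded, and 9.1.9 gives no censoring rule.

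The size rests on the assumed f and on what happens after the stop. At a true median of 8 months and f = 3-30%, the mean posterior moves from about 0.38 by almost nothing (few such patients, or early confirmation) to about 0.67 (f = 30%, censored; 0.68 if carried to death at 12 months). Futility stopping falls too, with the larger absolute drops at true medians of 4 and 6 months.

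Two stronger readings are not supported. The comparison is not with a fixed 8 months: λH has variance 40, an SD of √40 = 6.3 months. Nor can one say that an ineffective drug would be declared successful, because the plan sets no success cut-off; the effect is on the reported probability and on futility protection. If the historical 8 months used the same confirmation rule, some or all of the shift cancels. Section 8 does not say which rule it used.

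**What to change.** 1. Use one RFS definition, both time origin and event, in Sections 8 and 9, and define in Section 9 the progression that stops treatment under 4.3.
2. State that when a patient stops for progression, or starts other non-transplant anti-leukemia therapy, after a marrow above 5% blasts without confirmation, this is an RFS, EFS and CRd event dated at that marrow. Apply the rule at the futility looks as well.
3. Record relapse status, not only survival, at the existing off-treatment contacts until the data cut-off.
4. Report the primary posterior under confirmed relapse only as a sensitivity analysis, and state which relapse rule produced the historical 8 months.

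A separate rule for blood counts at or below 30% blasts is not needed, and an extra confirming marrow need not be made mandatory.

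The cost is amendment wording, one added item at contacts already planned, and one further run of the same posterior. No extra patients are needed. The downside is that a few unconfirmed marrows will be counted as relapse on investigator judgment; the sensitivity analysis shows how much that matters.
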